9.2.4. Study Medication Interruption and Discontinuation Criteria

9.2.4.1 Study Medication Interruption

Treatment with ATI-50002 Topical Solution should be temporarily interrupted in the event of severe adverse events considered related to ATI-50002, or in the event of one or more of the abnormal laboratory values in Table 2.

Table 2: Study Medication Interruption Criteria

Laboratory Test	Hold Study Medication if:	Resume Study Medication if:
WBC count	$< 2 \times 10^9/L$	$\geq 2.5 \times 10^9/L$
ANC	$< 1 \times 10^9/L$	$\geq 1.5 \times 10^9/L$
Lymphocyte count	$< 0.5 \times 10^9/L$	$\geq 0.75 \times 10^9/L$
Platelet count	$< 75 \times 10^9/L$	$\geq 100 \times 10^9/L$
Hemoglobin	$< 8 \text{ g/dL}$ or a decrease $> 2\text{ g/dL}$	$\geq 10 \text{ g/dL}$
AST or ALT	$> 3 \times \text{ULN}$	$< 2 \times \text{ULN}$ or within 20% of Baseline values
Serum creatinine	$> 2 \times \text{ULN}$	$< 1.5 \times \text{ULN}$ or within 10% of Baseline value

If a subject has one or more of the abnormal laboratory values noted in Table 2, the investigator or designee upon receipt and review of the central laboratory report should instruct the subject to hold study medication applications. The investigator or designee should ask the subject about symptoms, concomitant illnesses and medications and repeat the test(s) as soon as possible. The Medical Monitor must be notified of dose interruptions due to SAEs considered related to study medication or laboratory abnormalities noted in Table 2.

If the retest confirms the abnormal laboratory value, then the study medication should continue to be held followed by repeat testing once a week or sooner at the discretion of the investigator. The subject should be followed until the laboratory abnormality(s) return to normal or to baseline values.

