11.5. Safety Analyses

Safety analyses will include descriptive statistics calculated on the safety parameters using the safety population. The proportion of subjects with treatment-emergent adverse events will be tabulated and presented by treatment and Medical Dictionary for Regulatory Activities (MedDRA) System Organ Class. Vital signs and clinically significant abnormal laboratory results will also be tabulated and presented by treatment group.

Data from all randomized subjects will be presented and summarized. Safety summaries by study treatment group will include listings by study medication of adverse events incidences within each MedDRA System Organ Class, and changes from pre-application values in vital signs. Adverse event summaries will be presented by study medication showing the proportion of subjects experiencing adverse events, both overall and by MedDRA System Organ Class.

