#### Adverse Event (AE)

An AE is any untoward medical occurrence in a subject administered a study medication(s) and which does not necessarily have a causal relationship with the study medication. An AE can therefore be any unfavorable and unintended sign or symptom associated with the use of a study medication (including an abnormal laboratory finding), whether related to the study medication. Thus, any new, clinically significant worsening of an existing sign, symptom or disease, should be considered an AE. Every new episode or clinically significant worsening of a chronic condition (*e.g.*, headaches, seasonal allergies, depression, or hypertension) should be reported as a separate AE, even if the condition is reported in the subject's medical history.

Treatment-Emergent Adverse Event (TEAE)

For the interim analysis of the DB treatment period, any recorded AE that occurs on or after the initiation of study medication and within 31 days after the date of Visit 10 or after the date of last DB dose of study medication will be considered treatment-emergent. For the OLE period analysis, an AE that occurs on or after the initiation of OLE study medication and within 31 days after the date of last dose of study medication will be considered treatment-emergent.

Treatment-emergent Laboratory Abnormalities

A treatment-emergent laboratory abnormality is defined as a result in which the baseline value is within normal laboratory limits and the post-baseline value is outside normal laboratory limits. If the relevant baseline assessment is missing, then any post-baseline value outside normal laboratory limits is treatment-emergent.

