### **5.3.2. Clinical Laboratory Assessments, Vital Signs, and Physical Examination Findings**

Descriptive summaries of quantitative clinical laboratory results (hematology, chemistry, and urinalysis) and their change from baseline values will be presented by study visit and treatment group. Observed values of categorical urinalysis data will be displayed with frequencies and percentages. All laboratory data will be listed for individual subjects.

Treatment-emergent abnormal laboratory assessments will be based on the lab provided normal ranges. If the baseline laboratory assessment is normal and shifts to Low or High post-baseline, then the laboratory value is considered a TE abnormal laboratory value. For each protocol specified lab test, the number and percent of subjects reporting a TE abnormal lab will be reported.

All laboratory summaries will be limited to the tests specified in the protocol.

Descriptive summaries of vital signs and their change from baseline will be presented by study visit and treatment group and all vital signs will be listed.

Post-baseline PE findings will be listed.

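### The treatment-emergent laboratory tables cannot count a subject whose baseline is already abnormal, even when the value worsens past the protocol's own hold limits

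*SAP*

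**What the plan says.** SAP 3.3.6 defines a treatment-emergent laboratory abnormality as a result for which "the baseline value is within normal laboratory limits and the post-baseline value is outside normal laboratory limits". It adds one exception: "If the relevant baseline assessment is missing, then any post-baseline value outside normal laboratory limits is treatment-emergent". SAP 5.3.2 gives the same rule in other words ("If the baseline laboratory assessment is normal and shifts to Low or High post-baseline") and says that, for each test in the protocol, "the number and percent of subjects reporting a TE abnormal lab will be reported". Neither section says what happens when the baseline is known and already out of range.

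The laboratory tables listed in SAP 8.1 are of two kinds for each of hematology, chemistry and urinalysis: results with change from baseline by visit, and treatment-emergent abnormalities by visit. SAP 5.3.4 carries the same analyses into the open-label extension.

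Protocol 9.2.4.1 sets numeric limits in "Table 2: Study Medication Interruption Criteria"; treatment is to be interrupted for severe related adverse events "or in the event of one or more of the abnormal laboratory values in Table 2". Protocol 9.2.4.2 sets further limits for permanent discontinuation. Protocol 11.5 says that "clinically significant abnormal laboratory results will also be tabulated" by treatment group, with no condition on the baseline value.

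**The concern.** Safety is part of the primary objective. The treatment-emergent tables are the only listed laboratory tables that report how many subjects in each arm had an abnormal result. A definition that leaves out every abnormal baseline leaves out people in whom a worsening may matter. Under the SAP's general rule for by-visit percentages, they also stay in the denominator if they have a value at that visit.

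The entry criteria let such subjects in. Exclusion 13 removes an abnormal result only if it is clinically significant and the investigator thinks it makes the subject a poor candidate. Exclusion 14 sets numeric floors for neutrophils and platelets only. AST, ALT, creatinine, hemoglobin, total white cells and lymphocytes have no numeric entry limit. Liver enzymes are not an idle example: Protocol 2.1 reports mild ALT or AST elevations in three Phase 1 subjects given the oral prodrug, one of them recorded as a possibly related adverse event.

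**Working it through.** The plan states no figure on this point, so there is none to reproduce. The check applies the SAP rule and the Table 2 hold limits to the same pairs of values.

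**Rule.** With baseline B, post-baseline value P and normal range LLN to ULN, a result is treatment-emergent if (B is missing, or LLN ≤ B ≤ ULN) and (P < LLN or P > ULN). If B is known and out of range, the first bracket is false, so the result is not counted whatever P is. That includes B above ULN with P below LLN.

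**Table 2 hold limits used.** AST or ALT > 3 x ULN; creatinine > 2 x ULN; WBC < 2 and lymphocytes < 0.5 (x10^9/L); hemoglobin < 8 g/dL or a decrease of more than 2 g/dL.

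**Results.** ALT and creatinine are in multiples of ULN and need no outside reference range. The lower limits of normal for WBC, lymphocytes and hemoglobin are assumptions.

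| Test | B | P | SAP rule | Table 2 |
|---|---|---|---|---|
| ALT, x ULN | 0.9 | 1.05 | counted | no hold |
| ALT, x ULN | 1.2 | 3.5 | not counted | hold |
| ALT, x ULN | 1.2 | 6 | not counted | hold |
| ALT, x ULN | missing | 3.5 | counted | hold |
| Creatinine, x ULN | 1.1 | 2.2 | not counted | hold |
| WBC, LLN assumed 4 | 3.8 | 1.9 | not counted | hold |
| Lymphocytes, LLN assumed 1 | 0.9 | 0.45 | not counted | hold |
| Hemoglobin, LLN assumed 11.5 | 11.2 | 8.7 | not counted | hold |
| Hemoglobin, LLN assumed 13.5 | 13.2 | 10.7 | not counted | hold |

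Hemoglobin starts 0.3 g/dL below the assumed limit and falls by 2.5 g/dL; assumed limits of 12 and 13 give the same answer.

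**Does the protocol foresee abnormal baselines?** Yes. Table 2 allows AST or ALT dosing to resume below 2 x ULN "or within 20% of Baseline values". Reading that as up to 1.2 x B, the second route adds something only if 1.2 x B ≥ 2, that is B ≥ 2/1.2 = 1.67 x ULN. The matching creatinine rule (below 1.5 x ULN, or within 10% of baseline) adds something only if B ≥ 1.5/1.1 = 1.36 x ULN. Both are abnormal baselines.

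**Is the gap filled elsewhere?** SAP 8.1 lists no table of shifts from baseline category, no count of subjects crossing a Table 2 or 9.2.4.2 limit, and no table of clinically significant laboratory results by arm. SAP section 6 nevertheless states that the SAP's analyses agree with the protocol's.

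**The case against.** The strongest reply is that these cases are not lost. SAP section 5 includes the minimum and maximum in its descriptive statistics, and SAP 5.3.2 applies such summaries to values and changes by visit and arm, so a rise to 6 x ULN at an analysed visit would set, or lie below, the printed maximum. Protocol 8.4.3 requires any out-of-range result that the investigator finds clinically significant after first dosing to be reported as an adverse event, whatever the baseline; it then reaches the adverse event tables by arm. All laboratory data are listed, with a separate listing of abnormalities. Section 8 of the SAP is headed as proposed tables.

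All of this stands, and it rules out a reading that a reader might reach: that worsening from an abnormal baseline goes unreported. It is uncounted in the treatment-emergent laboratory tables only. What these routes do not give is an objective count. A maximum shows one extreme, not how many subjects crossed a limit or where they started, and SAP 3.3.7 summarizes only the result nearest the target day in each window. Listings give no rate by arm. The adverse event route rests on judgement, whereas the Table 2 limits are numeric.

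Three other stronger readings also fail:

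- **A bias between arms.** The rule is the same in every randomized arm. It lowers sensitivity; the documents do not show that it favors one arm.
- **A known number of missed cases.** If 5% to 20% of subjects were abnormal at baseline on some test (an assumption with no support in the documents), 0.05 x 40 = 2 to 0.20 x 40 = 8 per arm could not be counted on it. That is a ceiling on missed worsenings, not an estimate; the true number could be zero.
- **That any worsening should count.** ALT moving from 1.20 to 1.21 x ULN would then be treatment-emergent, which adds measurement noise.

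The entry criteria also narrow the gap. For neutrophils and platelets, exclusion 14 is meant to keep out low values, although baseline is the last value before dosing and can differ from screening.

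**Conclusion.** The point holds for the treatment-emergent laboratory tables. Followed exactly, SAP 3.3.6 and 5.3.2 count a trivial step past the upper limit and omit changes that meet the protocol's own criteria for holding treatment, whenever the baseline was already abnormal. The ALT and creatinine examples need no outside figure; the hematology examples rest on the assumed reference limits shown above. Separately, the tabulation promised in Protocol 11.5 has no dedicated counterpart in the SAP list. The adverse event tables cover it in part, through investigator reporting.

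The size cannot be computed, because the documents give no frequency of abnormal baselines or of later worsening; the number with an abnormal baseline is the upper bound for each test. It is a defect in safety reporting that should be corrected. It does not touch the efficacy analysis.

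**What to change.** In SAP 3.3.6 and 5.3.2, keep the present rule for normal and missing baselines. Add that an abnormal baseline also counts when a post-baseline value moves to the opposite abnormal direction, or newly crosses an existing limit in Protocol Table 2 or 9.2.4.2 (or reaches a pre-specified higher grade). A numerical worsening alone should not count.

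Add to SAP 8.1, and to 8.2 for the extension:

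- shift tables of baseline Low, Normal or High against the worst post-baseline category, using scheduled and unscheduled results;
- counts by arm of subjects crossing each existing Table 2 limit;
- the table by arm of clinically significant abnormal laboratory results named in Protocol 11.5.

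The cost is some SAP wording, a few extra tables from data already collected, and slightly higher reported abnormality rates. No clinical limit changes.

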**3.3.7. Presentations by Study Visit**

Results from efficacy assessments and safety will be summarized by study visit and treatment group. For the DB period, all assessments will be assigned to an analysis visit window using the study day ranges described in Table 1. All study days up to and including Day 1 (DB) are considered the baseline eligible analysis visit window. The last non-missing assessment in the baseline analysis visit window will be used for the baseline summary presentations. If assessments are collected multiple times within a given analysis visit window, the result closest to the target study day, regardless of whether scheduled or unscheduled, will be used for summary presentations. If two measurements have the same distance to the target study day, the first assessment will be used in the summary presentations. All assessments will be presented in the listings.

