6.4. Duration of the Study

Double-blind Period

The anticipated time for study enrollment is 6 months. The duration of the screening period could be up to 30 days. Once randomized, the maximum duration of double-blind study treatment from Baseline (Visit 2) to the post-treatment follow-up visit at Week 28 (Visit 11) is anticipated to be a maximum of 200 days (197 days + 3-day window).

Open-Label Extension

The maximum duration of the of study treatment in the OLE is 176 days (168 days + 7-day window). The maximum duration of the study participation from entry into the OLE to completion of the post-treatment follow up visit is 204 days.

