#### **Double-blind (DB) Period:**

A total of 120 subjects will be randomized in a 1:1:1 ratio:

- Vehicle Topical Solution BID for 24 weeks (6 months)
- ATI-50002 Topical Solution, 0.12%, BID for 24 weeks (6 months)
- ATI-50002 Topical Solution, 0.46%, BID for 24 weeks (6 months)

During the screening period, subjects will be assessed for eligibility into the study. Subjects will apply up to 4 mL of study medication to the entire scalp or patchy areas with a ½” margin twice a day for 24 weeks. Assessment of response to treatment will be performed at Week 4 (Visit 5), Week 8 (Visit 6), Week 12 (Visit 7), Week 16 (Visit 8), Week 20 (Visit 9), Week 24 (Visit 10), and post-treatment Week 28 (Visit 11). Safety and tolerability will be evaluated at each study visit by assessment of adverse events and vital signs, and at select visits, ECGs and clinical laboratory tests will be completed. The primary analysis will be conducted after all subjects complete Visit 10 or Visit 11 of the double-blind period.

Subjects who complete Visit 10 or Visit 11 (Week 24 or 28) will be eligible to enter a 28 week OLE. Subjects who decline or are not eligible for the OLE should be seen for the Visit 11 (Post-treatment) assessments.

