**1.2. SCHEDULE OF ASSESSMENTS**

Double-Blind Treatment Period	Screening	Baseline	Treatment								Post-Treatment
	Visit 1	Visit 2	Visit 3	Visit 4	Visit 5	Visit 6	Visit 7	Visit 8	Visit 9	Visit 10	Visit 11
Week		0	1	2	4	8	12	16	20	24	28
Treatment Day	-30 to 0	1	8	15	29	57	85	113	141	169	197
Treatment window (days)	N/A	N/A	±3	±3	±3	±3	±3	±3	±3	±3	±3
Informed consent/assent 	X									X 	X 
Inclusion/exclusion criteria	X	X									
Physical exam 	X									X	
Demographics & medical history	X										
Alopecia Areata History	X										
Vital Signs 	X	X	X	X	X	X	X	X	X	X	X
Clinical CBC, Chemistry, Virology, Serum Pregnancy, Urinalysis 	X 	X		X	X	X	X	X	X	X	X
Urine pregnancy test 		X			X	X	X	X	X	X	X
ECG	X	X		X	X	X	X	X	X	X	X
SALT Score (prior to ALODEX) 		X			X	X	X	X	X	X	X
ALODEX Score (after SALT) 		X			X	X	X	X	X	X	X
Target Scalp Patch Identification 		X									
Assessment of hair quality 		X			X	X	X	X	X	X	X
Scalp-ClinRO All Patches, Target Patch 		X			X		X			X	
Scalp-PRO All Patches, Target Patch 		X			X		X			X	
Physician Global Impression of Severity (PhGIS) 		X			X		X			X	
Physician Global Impression of Change (PhGIC)										X	
Subject Global Impression of Severity (PhGIS) 		X			X		X			X	
Subject Global Impression of Change (PhGIC)										X	
Subject Global Impression Treatment Satisfaction (SGITS)							X			X	
DLQI 		X			X		X			X	
Alopecia Impact Assessment-Patient Reported Outcome (AIA-PRO) 		X			X		X			X	
Photography (complete scale and target patch) 		X			X	X	X	X	X	X	X
Subject Randomization		X									
Subject instructions 		X	X	X	X	X	X	X	X	X	
Dispense collect, weigh study medications 		X	X	X	X	X	X	X	X	X	
In office study medication applications 		X									
Concomitant therapies		X	X	X	X	X	X	X	X	X	X
Adverse events		X	X	X	X	X	X	X	X	X	X

Open-Label Extension	Open-Label Treatment							Post Treatment
	OLE Visit 1			OLE Visit 2	OLE Visit 3	OLE Visit 4	OLE Visit 5	OLE Visit 6
	Week	Visit 11 (Week 28) was:		2	4	12	24	28
Treatment Day	OLE Visit 1 occurs at Visit 10 or 11	≤ 30 Days	>30 Days	15	29	85	169	197
Treatment window (days)	NA	NA	NA	±3	±3	±7	±7	±7
Informed consent/assent 	X	X	X					

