#### Study Visit

Study Visit is the nominal visit as recorded on the CRF.

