### **5.2.2. Primary Efficacy Analysis**

Descriptive statistics for the SALT score, change, and percent change from baseline will be presented for each scheduled analysis visit. Percent change from baseline in SALT over time up to Week 24 will be analyzed using a mixed effect for repeated measures (MMRM) model. This primary analysis will utilize the score with imputation for LOCF and will be based on the ITT population. The model will include fixed effect terms for treatment, study visit, baseline SALT score group (<50, >=50), and treatment by SALT group interaction. Within-subject variability will be modeled using a compound symmetry covariance structure. The least squares mean (LS Mean) percent change from baseline in the SALT score at each visit, estimated from the MMRM model, with the estimated standard error and 95% confidence interval (CI), will be presented in tabular and graphic format. The difference in the adjusted means between treatment groups and the associated 95% CI of the difference will be provided.

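### SAP Table 1 stops at Day 182, so an on-schedule Week 28 visit has no window in the double-blind by-visit summaries, and a Visit 10 held on Day 183 or later is unassigned

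*SAP*

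**What the plan says.** SAP section 3.3.7 opens with a general rule: "Results from efficacy assessments and safety will be summarized by study visit and treatment group". It continues: "For the DB period, all assessments will be assigned to an analysis visit window using the study day ranges described in Table 1". Table 1 then gives rows from baseline to Week 24. The Week 24 row has target Day 169 and range Days 155 to 182. There is no Week 28 row. The same section sends every assessment to the listings.

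SAP section 3.3.6 defines the term differently: "Study Visit is the nominal visit as recorded on the CRF".

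Week 28 is a planned assessment. The list of response assessments in SAP section 1.1 ends with "Week 24 (Visit 10), and post-treatment Week 28 (Visit 11", and protocol section 6.1 includes the same visit. The schedules (protocol section 6.3, SAP section 1.2) place Visit 11 at Day 197 with a tolerance of 3 days and collect SALT, ALODEX, hair quality, laboratory tests, ECG and vital signs there.

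The primary model has a stated end point (SAP section 5.2.2): "Percent change from baseline in SALT over time up to Week 24 will be analyzed using a mixed effect for repeated measures (MMRM) model". Missing assessments are filled by LOCF (SAP section 3.3.4). Section 5.2.3 repeats the analysis on observed data without imputation.

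**The concern.** A windowing rule that covers all double-blind assessments, paired with a table that ends before the last scheduled visit, discards data the trial set out to collect. Neither document says that Week 28 is to be listed only, and SAP section 6 declares the planned analyses consistent with the protocol.

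Two things are at stake. First, the post-treatment laboratory, vital-sign, ECG, SALT, ALODEX and hair pull results would have no row in the by-visit tables. This includes the treatment-emergent laboratory abnormality tables, which SAP section 8.1 titles by visit. Second, a Visit 10 held after Day 182 would have a measured SALT score that the primary analysis ignores in favour of a carried-forward value, normally Week 20. The same subject may count as having completed Visit 10 for the per-protocol population (SAP section 4.3), and the same measurement is the end-of-double-blind reference in the open-label summaries (SAP section 5.2.9).

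The wording also leaves room for two programmers to differ. One could window everything and drop Week 28. The other could follow the nominal definition of study visit and keep it.

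**Working it through.** **Inputs.** Target days 1, 8, 15, 29, 57, 85, 113, 141, 169 and 197, with a tolerance of ± 3 days at Visits 10 and 11, come from the schedules. The window ranges come from SAP Table 1.

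**1. How the Week 24 bound arises.** The printed bounds follow midpoints between adjacent targets.
- Lower bound: (141 + 169)/2 = 155, as printed.
- Upper bound: (169 + 197)/2 = 183. A window that stops the day before ends at Day 182, as printed.

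From Week 8 to Week 24 every window runs from target − 14 to target + 13; for Week 24 this is 169 − 14 = 155 and 169 + 13 = 182. The cut-off therefore sits where a Week 28 window would begin. That fits an omitted row but does not prove one.

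**2. Visit 11 against Table 1.** Permitted days: 197 − 3 = 194 to 197 + 3 = 200. The last window ends at Day 182. Days covered: 0 of 7.

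**3. Visit 10 against Table 1.** Permitted days: 169 − 3 = 166 to 169 + 3 = 172. All lie within Days 155 to 182. Days covered: 7 of 7. The first unassigned day is Day 183, which is 183 − 169 = 14 days after target and 183 − 172 = 11 days past the protocol limit.

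**4. What happens to a Visit 10 on Day 183 or later.** The Week 24 window is empty unless another assessment falls in it. In the LOCF analysis the subject stays in, with an earlier value as Week 24. In the observed-data analyses the subject has no Week 24 record.

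**5. Which outputs depend on Table 1.**

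| Output | Effect of the missing window |
|---|---|
| SALT, ALODEX and hair pull by analysis visit | No Week 28 row |
| Laboratory, vital signs and ECG by visit | No Week 28 row if windowed; kept if the nominal visit governs |
| Primary MMRM | Ends at Week 24; changed only by a Visit 10 after Day 182 |
| TEAE counts | None; they use a 31-day rule, and the nominal gap from Visit 10 to Visit 11 is 197 − 169 = 28 days |
| QT and QTcF threshold counts | None; not tied to Table 1 |
| Open-label summaries | None; nominal visits, with Visit 10 as reference |
| Listings | None; all assessments are shown |

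**6. Extending the table.** The same −14/+13 pattern at target 197 gives 197 − 14 = 183 to 197 + 13 = 210. This covers Days 194 to 200. By itself, however, the row would also label a Visit 10 held on Days 183 to 210 as post-treatment Week 28, so a precedence rule is needed.

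**The case against.** The strongest reply is that this is a wording gap in descriptive output. The dated efficacy endpoints are all at Week 24, the primary model stops there by design, and no objective concerns durability after stopping treatment. Subjects may enter the open-label extension at Visit 10, while those who decline or are ineligible are to be seen at Visit 11. Week 28 attendees are therefore selected after randomisation, and a by-arm efficacy comparison among them would not be a randomised one. All of this stands, and it is why the Week 28 row should be descriptive only.

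A second reply is that the loss is not certain. Study visit is defined as nominal, SAP section 5.3.2 summarises laboratory and vital-sign data by study visit, and section 5.3.3 summarises ECG change at each scheduled evaluation. SAP section 3.3.6 also sets Day 1 (OLE) at the Visit 10 date for everyone entering the extension, so their Visit 11 data might be claimed for the open-label period, where nominal visits apply. This stands as evidence of ambiguity but does not resolve it: the windowing sentence covers all double-blind assessments, and Visit 11 is not among the open-label visits in the schedule.

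A third reply is that any window needs a cut-off, and 10 days of slack beyond the protocol limit (182 − 172) is generous. That is fair, and it limits the size of the late-Visit-10 problem. It does not explain why an observed value should give way to a carried-forward one when the measurement preceded any open-label dose.

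A reader might infer that Week 28 and late Visit 10 data vanish from every by-visit analysis, or that post-treatment safety by arm cannot be seen. The documents support neither. Open-label summaries use nominal visits, a subject with a late Visit 10 remains in the LOCF analysis, TEAEs are tabulated by arm without windows, and the listings keep everything.

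**Conclusion.** The gap is real and limited. Read literally, the rule leaves every on-schedule Visit 11 (Days 194 to 200, 0 of 7 days covered) out of the windowed double-blind by-visit summaries of SALT, ALODEX, hair pull, laboratory tests, vital signs and ECG. A Visit 10 on Day 183 or later loses its observed Week 24 value to LOCF in the primary analysis and has no Week 24 record in the observed-data analyses.

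The first part concerns everyone who attends Visit 11 on schedule; the documents do not say how many that will be. The second part is likely to touch few subjects, because it needs a visit at least 11 days past the permitted range; no count or expected rate is given. It would be wrong to infer that the primary result is generally at risk: for any Visit 10 held by Day 182 it is unchanged.

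The conclusion assumes that the windowing sentence overrides the nominal definition of study visit. If the nominal definition governs, the Week 28 loss disappears for the summaries described by study visit, and the remaining defect is that the SAP does not say so. Either way the text should be corrected before unblinding.

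**What to change.** 1. Add a descriptive row to Table 1: Week 28 (post-treatment), target Day 197, range from Day 183 (for example 183 to 210). Limit it to assessments before any open-label dose and exclude any nominal Visit 10. Add a note that attendees are a selected subset and that no by-arm efficacy inference is intended. Define the cut-off by the recorded first open-label application. Day 1 (OLE) will not serve, because the SAP sets it at the Visit 10 date and it would remove Visit 11 for all extension entrants.
2. State that a nominal Visit 10 after Day 182 and before any open-label dose is used for Week 24 when the Week 24 window is empty, and is never counted as Week 28. Confining the rule to visits after Day 182 leaves early-termination Visit 10 assessments in the window of the day they were done.
3. Reconcile the nominal definition of study visit in SAP section 3.3.6 with the windowing rule in section 3.3.7, and say which one governs each by-visit table.

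If Week 28 was meant to be listed only, one sentence saying so replaces item 1. The cost is one table row and a few sentences, with matching programming of the by-visit tables. No new data are needed.

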#### Section 14.3 Safety

- 78. Table 14.3.1.1 Overall Summary of Adverse Events, Safety Population
- 79. Table 14.3.1.2 Treatment-Emergent Adverse Events by System Organ Classification, Preferred Term, and Greatest Severity, Safety Population
- 80. Table 14.3.1.3 Treatment-Emergent Adverse Events by System Organ Classification and Preferred Term, Safety Population
- 81. Table 14.3.1.4 Treatment-Emergent Serious Adverse Events by SOC and PT, Safety Population
- 82. Table 14.3.1.5 Treatment-Emergent Adverse Events Related to Study Drug by SOC and PT, Safety Population

83. Table 14.3.1.6 Treatment-Emergent Adverse Events Leading to Discontinuation of Study Drug by SOC and PT, Safety Population
84. Table 14.3.1.7 Study Drug Related Treatment-Emergent Adverse Events Leading to Discontinuation of Study Drug by SOC and PT, Safety Population
85. Table 14.3.4.1.1 Summary of Hematology Results and Change from Baseline by Visit, Safety Population
86. Table 14.3.4.1.2 Summary of Treatment-Emergent Abnormal Hematology by Visit Safety Population
87. Table 14.3.4.2.1 Summary of Serum Chemistry Results and Change from Baseline by Visit, Safety Population
88. Table 14.3.4.2.2 Summary of Treatment-Emergent Abnormal Serum Chemistry by Visit, Safety Population
89. Table 14.3.4.3.1 Summary of Urinalysis Results and Change from Baseline by Visit, Safety Population
90. Table 14.3.4.3.2 Summary of Treatment-Emergent Abnormal Urinalysis by Visit, Safety Population
91. Table 14.3.5.1.1 Summary of ECG Results and Change from Baseline by Visit, Safety Population
92. Table 14.3.5.1.2 Proportion of Subjects with Abnormal ECG Interpretations by Visit, Safety Population
93. Table 14.3.5.2.1 Summary of Vital Signs and Change from Baseline, Safety Population

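### The one-result-per-window rule in SAP 3.3.7 can drop out-of-range laboratory values from the by-arm counts of treatment-emergent abnormalities, because the SAP states no any-value or worst-value rule

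*SAP*

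**What the plan says.** SAP 3.3.7 sets its scope broadly: "Results from efficacy assessments and safety will be summarized by study visit and treatment group". It continues: "For the DB period, all assessments will be assigned to an analysis visit window using the study day ranges described in Table 1". Within a window one result is kept: "the result closest to the target study day, regardless of whether scheduled or unscheduled, will be used for summary presentations". Ties are settled by order: "If two measurements have the same distance to the target study day, the first assessment will be used in the summary presentations". Results that are not selected survive elsewhere: "All assessments will be presented in the listings". For the open-label extension the SAP uses the nominal visit, so the selection rule concerns the double-blind period only.

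SAP 3.3.6 calls a laboratory result treatment-emergent abnormal when baseline is within normal limits and the later value is not. SAP 5.3.2 adds that, for each test, "the number and percent of subjects reporting a TE abnormal lab will be reported". Neither section says which post-baseline results feed that count. The list of outputs in SAP 8.1 gives the format, for example "Summary of Treatment-Emergent Abnormal Hematology by Visit" (Table 14.3.4.1.2). The chemistry and urinalysis tables (14.3.4.2.2 and 14.3.4.3.2) are titled the same way.

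Protocol 9.2.4.1 explains why several results can fall in one window. A value meeting Table 2 leads to a hold and a prompt repeat. If the repeat confirms it, "the study medication should continue to be held followed by repeat testing once a week or sooner at the discretion of the investigator".

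**The concern.** Choosing by calendar distance suits means and changes at a visit. It suits a count of abnormalities poorly, because it ignores whether the discarded value was out of range. Extra results arise mainly in subjects who already had an abnormal value, so the rule acts most often on the subjects whom these tables are meant to show.

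Compared with a count over all post-baseline results, keeping one result per window can lose abnormal subjects but cannot add any. Safety against vehicle is part of the primary objective. If abnormal values were more frequent on active drug, the absolute difference between arms could be understated.

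**Working it through.** The plan gives no figure to reproduce here. The check applies its selection rule to the sequences of draws that the protocol can produce.

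**Inputs**
- SAP Table 1: Week 8 has target Day 57 and range Days 43–70. Week 12 has target Day 85 and range Days 71–98.
- Schedule of assessments: scheduled visits may fall within ±3 days of target.
- Protocol 9.2.4.1: repeat as soon as possible, then weekly or sooner.
- Assumed, because the documents give no timing data: scheduled draws are equally likely on each of the seven allowed days, and the first retest is equally likely on each day of the stated range.

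**Route 1: a retest displaces an abnormal scheduled draw.** Let v be the draw day minus the target day, and k the days to the first retest. The retest is selected when |v + k| < |v|. For v < 0 this means k ≤ 2|v| − 1. For v ≥ 0 it never happens, and ties keep the first result.

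| Week 8 draw | v | Gaps k that displace | Count, k = 1–7 | Count, k = 3–7 |
|---|---|---|---|---|
| Day 54 | −3 | 1 to 5 | 5 | 3 |
| Day 55 | −2 | 1 to 3 | 3 | 1 |
| Day 56 | −1 | 1 | 1 | 0 |
| Days 57–60 | 0 to +3 | none | 0 | 0 |
| Total | | | 9 of 7 × 7 = 49 (18%) | 4 of 7 × 5 = 35 (11%) |

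A weekly retest after the first lands at least −3 + 1 + 7 = 5 days past the target, so it is never closer than the scheduled draw.

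Displacement is not yet loss. The share lost at that visit is the displacement share times p, the probability that the selected value is within the normal range. The documents give no p. With p from 0 to 1, the loss runs from 0 to 9/49, or from 0 to 4/35.

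**Route 2: an abnormal unscheduled draw between visits.** Take draws on Days 57, 64, 66, 73, 80 and 85, with Days 57 and 85 normal and scheduled.
- Week 8 window: distances are 0 (Day 57), 7 (Day 64) and 9 (Day 66), so Day 57 is kept.
- Week 12 window: distances are 12 (Day 73), 5 (Day 80) and 0 (Day 85), so Day 85 is kept.

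All four unscheduled values are dropped, and these tables count the subject as abnormal at neither visit.

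**A case with no subject lost.** Take draws on Days 57, 64, 71, 78 and 85, abnormal from Day 57. Days 57 and 85 are kept and three of the five results are dropped, but the subject is still counted at Week 8.

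**The case against.** Several points on the other side stand, in whole or in part.

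- *Results are not subjects.* This stands. Dropping retests from a window that keeps its abnormal result leaves that visit's count unchanged. A reader might take 9 of 49 as the share of abnormal subjects missed. The documents do not support that, because the replacing value must also be normal. Clearing a hold limit is not enough: Table 2 holds drug for AST or ALT above 3 × ULN and allows resumption below 2 × ULN, so a retest between 1 and 2 × ULN is still counted as abnormal.
- *Very quick retests are unlikely.* This largely stands. Samples go to a central laboratory (Protocol 8.4.3), and the hold follows receipt and review of its report. A gap of only 1 to 3 days would give 7 of 21, but that is the least plausible timing. The 3-to-7-day figure is the more cautious one.
- *SAP 5.3.2 carries no visit qualifier, and the definition in 3.3.6 is worded per result.* An any-value count is therefore a possible reading. However, 3.3.7 covers safety, and all three tables are titled by visit. Two programmers could reasonably produce different counts, which is itself a reason to state the rule.
- *Other outputs capture these values.* This stands in part. Clinically significant results are reported as adverse events, and those tables are not windowed. That route depends on investigator judgement, while the laboratory tables use fixed limits. Listings give no rates by arm. Protocol 11.5 promises a tabulation of clinically significant abnormal laboratory results by treatment group, but SAP 8.1 lists no dedicated table.
- *ECGs are different.* This stands. A reader might extend the point to ECG interpretations and QTcF categories. The hold-and-retest scheme is for laboratory tests only, listed ECG findings lead to withdrawal (Protocol 9.2.3), and SAP 5.3.3 does not plan the QTcF categories by visit.

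**Conclusion.** The point holds as a gap in the counting rule. Followed as written, the SAP can leave an out-of-range double-blind laboratory value out of the by-arm abnormality counts by either route above.

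For an abnormal value drawn at a scheduled visit, loss is at most 9 of 49 under the assumed timing, or 4 of 35 with the slower retest. Loss through unscheduled draws is not covered by those bounds. The documents give no abnormality rates, no chance of normalisation and no frequency of unscheduled tests, so the effect on actual counts is unknown.

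A reader might also infer that the tables hide how many subjects crossed a hold limit, or how deep a nadir went. The treatment-emergent tables are built on laboratory normal ranges, so they would show neither under any selection rule. Nor do the documents establish that the comparison with vehicle will in fact be biased: the direction is clear if losses occur, but the amount is not.

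**What to change.** Before unblinding, make three changes to the SAP.

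1. In 3.3.7, restrict the closest-to-target selection to by-visit descriptive summaries of values and changes.
2. In 5.3.2, state that a subject has a treatment-emergent laboratory abnormality if any post-baseline double-blind result qualifies, scheduled or unscheduled.
3. Add an any-time-on-treatment row to Tables 14.3.4.1.2, 14.3.4.2.2 and 14.3.4.3.2. The same row may be added to ECG Table 14.3.5.1.2 for consistency, although the case there is weaker.

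The cost is SAP wording and minor programming. No new data are needed. Reported abnormality rates may come out slightly higher.
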